2.2 Overall Study Design and Investigational Plan

This is a phase III, multicentre, open-label, non-comparative, repeat dose study to evaluate the efficacy and safety of triptorelin 6-month formulation (22.5 mg) administered subcutaneously in participants with locally advanced and/or metastatic prostate cancer previously treated and castrated with a GnRH analogue.

Approximately 145 participants will be assigned to triptorelin embonate 22.5 mg (6-month formulation) to be administered on Day 1 and Day 169. Note: participants must receive study intervention on Day 1 in accordance with the treatment schedule of their previously received GnRH analogue therapy.

[figure not shown]
The study will consist of a 4-week screening period, during which participants with prostate cancer will be screened for eligibility. On Day 1, all eligible participants will receive a single open-label administration of study intervention. Following treatment on Day 1, visits will occur on Day 3, Day 7, Day 29, Day 85, Day 141, Day 169 (second administration), Day 171, Day 175, Day 253, Day 309 and Day 337. (Note: if necessary, participants can request home visits, except for visits where study intervention is to be administered).

Participants will be considered to have completed the study when final procedures and assessments have been performed at the Day 337 visit. Participants who withdraw from the study before the completion of the Day 337 visit will have early discontinuation procedures and assessments performed at their final visit.

Associated Procedure / Instruction Reference	319480-SOP
Form Reference	080091-FOR v7.0

The study design is illustrated in [Figure 1](#).

Figure 1 Study Schema

D=day; ED=early discontinuation; EoS=end of study

Participants will receive a subcutaneous injection of triptorelin embonate 22.5 mg (6-month formulation) on Day 1 and Day 169.

2.3 Sample Size Determination and Power

This single-arm study is designed to demonstrate that the percentage of participants remaining castrated (maintenance of castration defined as testosterone <1.735 nmol/L (50 ng/dL) at Day 29, Day 85, Day 141, Day 169, Day 253, Day 309 and Day 337) during the study is greater than 90%. Considering an observed castration maintenance in 97% of participants, 130 eligible participants are required to demonstrate the efficacy of the triptorelin 6-month formulation with approximately 90% power and a one-sided alpha of 0.025 using an exact binomial test. The objective will be achieved if the lower bound of the 95% confidence interval (CI) of the observed rate is greater than 90%.

Considering a drop-out rate of 10%, 145 participants will be included in the study.

2.4 Randomisation and Blinding

This is a non-randomised, open-label study. Therefore, no procedure for blinding is applicable.

2.5 Schedule of Assessments

Schedule of assessments is presented in section 1.3 from the protocol.

2.6 Change from Statistical Section of the Protocol

There is no change from the statistical section of the protocol.

Associated Procedure / Instruction Reference	319480-SOP
Form Reference	080091-FOR v7.0

IPSEN GROUP

CONFIDENTIAL

D-FR-52014-245

SAP Final: Version 1.0: 30 January 2023

PAGE 11/43

3 PLANNED ANALYSES

3.1 Data Monitoring

No independent Data Monitoring Committee will be used in this study.

3.2 Interim Analysis / Primary Analysis

No interim analysis will be performed.

3.3 Final Analysis

Planned analyses will be done when all participants complete study and after database lock.

Associated Procedure / Instruction Reference	319480-SOP
Form Reference	080091-FOR v7.0

4 ANALYSIS SETS

Screened Set

The screened set will contain all participants who signed an informed consent for this study. In case of re-screening, the participant will be counted once only in the screened set. The previous site and assigned subject numbers will be collected to link the first and second screening data.

Enrolled Set

The enrolled set will contain all participants who were enrolled to study treatment. A participant will be considered as enrolled if he has signed the informed consent form and is assigned to treatment.

Intent-to-Treat Set

The intent-to-treat (ITT) Set will contain all participants who signed an informed consent form and received at least one administration of study intervention and have a serum testosterone level <1.735 nmol/L (50 ng/dL) on Day 1 (pre-dose measurement).

Full Analysis Set

The full analysis set (FAS) will contain all participants who signed an informed consent form and received two administrations of study intervention and completed all visits for testosterone measurement (Day 29, Day 85, Day 141, Day 169, Day 253, Day 309 and Day 337). Note, a participant will be included in the FAS if his testosterone measurement is ≥ 50 ng/dl before the end of treatment, end of study or withdrawn from study, whichever is earlier.

Per Protocol Set

The per protocol (PP) set will contain all participants from the FAS who did not experience any major protocol deviations that may interfere with efficacy evaluation (refer to section 5.3 for details regarding the management of deviations).

Safety Set

The safety set will contain all participants who receive at least one dose of study intervention.

Associated Procedure / Instruction Reference	319480-SOP
Form Reference	080091-FOR v7.0

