
 To demonstrate the safety profile of triptorelin embonate 22.5mg 6-month formulation administered subcutaneously 	
 Incidence of TEAEs (including local tolerability) throughout the study i.e. up to Day 337 Change from baseline in clinical safety laboratory parameters (blood chemistry and haematology) at Day 337 Change from baseline in physical examination at Day 169 and Day 337 Change from baseline in ECG at Day 337 Change from baseline in vital signs (blood pressure and heart rate) at each visit up to Day 337

AE=adverse event; ECG=electrocardiogram; PSA=prostate-specific antigen; TEAE=treatment emergent adverse event

Note: A list of laboratory parameters to be assessed during the study are presented in Appendix 10.2.

The primary estimand for the primary endpoint is described below. The treatment will be triptorelin 6-month formulation administered subcutaneously. The population will comprise

participants with locally advanced and/or metastatic prostate cancer previously treated and castrated with a GnRH analogue as specified in the inclusion and exclusion criteria (Sections 5.1 and 5.2), respectively, that have received two scheduled treatment intervention doses (i.e. Day 1 and Day 169) and have completed all visits for measurement of testosterone.

The variable for the primary estimand will be castration maintenance rate during the study, which is defined as percentage of participants castrated (testosterone <1.735 nmol/L (50 ng/dL)) at Day 29, Day 85, Day 141, Day 169, Day 253, Day 309 and Day 337, with two complete study intervention administrations. Secondary estimands include analyses without using the visit window and/or using the ITT population where missing data will be considered a non-responder maybe conducted. Further details of the estimand will be specified in the SAP.

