
 To demonstrate the effect of triptorelin embonate 22.5 mg 6-month formulation administered subcutaneously to suppress the 'acute-on-chronic' effect following the administration of the second dose 	
 Percentage of participants castrated on Day 3 and Day 7 after each injection administered on Day 1 and Day 169 (castration defined as testosterone <1.735 nmol/L (50 ng/dL))

 To demonstrate the effect of triptorelin embonate 22.5 mg 6-month formulation administered subcutaneously in the maintenance of PSA 	
 Percent change in PSA from baseline (prior to injection) at Day 169 and Day 337 (Percent change in PSA defined as the absolute value of difference between the PSA values at Day 169 and Day 337 and the baseline value divided by the baseline value)

Associated Procedure / Instruction Reference	319480-SOP
Form Reference	080091-FOR v7.0

Objectives	Endpoints

 To demonstrate the safety profile of triptorelin embonate 22.5mg 6-month formulation administered subcutaneously 	
 Incidence of TEAEs (including local tolerability) throughout the study i.e. up to Day 337 Change from baseline in clinical safety laboratory parameters (blood chemistry and haematology) at Day 337 Change from baseline in physical examination at Day 169 and Day 337 Change from baseline in ECG at Day 337 Change from baseline in vital signs (blood pressure and heart rate) at each visit up to Day 337

AE=adverse event; ECG=electrocardiogram; PSA=prostate-specific antigen; TEAE=treatment-emergent adverse event

Note: A list of laboratory parameters to be assessed during the study are presented in Protocol Appendix 10.2.

- Hypotheses**

Hypotheses for this study are defined below.

The primary objective of this study is to evaluate the efficacy triptorelin embonate 22.5 mg (6-month formulation) administered subcutaneously in maintaining serum testosterone castrate levels during the study (maintenance of castration defined as testosterone <1.735 nmol/L (50 ng/dL) at Day 29, Day 85, Day 141, Day 169, Day 253, Day 309 and Day 337) with two complete study intervention administrations. Thus, the null hypothesis to be tested is as follows:

Null hypothesis: percentage of participants castrated (serum level of testosterone <1.735 nmol/L) from date of first dose to Day 337 is less than or equal to 90%.

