5.7.2 Analysis of Primary Efficacy Endpoint

5.7.2.1 Primary Efficacy Endpoint, Treatment Effect and Estimand Definition

To assess the primary objective, the primary estimand will be defined by the following attributes:

- Population: participants with locally advanced and/or metastatic prostate cancer previously treated and castrated with a GnRH analogue as defined by the listed Inclusion/Exclusion criteria in sections 5.1 and 5.2 of the protocol, respectively.
- Variable/Endpoint: castration maintenance rate during the study defined as percentage of participants castrated (testosterone < 1.735 nmol/L (50 ng/dL)) at Day 29, Day 85, Day 141, Day 169, Day 253, Day 309 and Day 337, with two complete study intervention administrations.
- Key Intercurrent event (ICE):
 - (a) ICE 1 - Subjects discontinued from study prior to Day 337 without evidence of inadequate testosterone suppression (testosterone measurement \geq 50 ng/dL)
The testosterone values of these participants will not be considered for the main analysis (principal stratum strategy).
 - (b) ICE 2 - Subjects with at least one planned testosterone measurement missing on or prior to Day 337 without evidence of inadequate testosterone suppression (testosterone measurement \geq 50 ng/dL)
The testosterone values of these participants will not be considered for the main analysis (principal stratum strategy).

Associated Procedure / Instruction Reference	319480-SOP
Form Reference	080091-FOR v7.0

(c) ICE 3 - Subjects discontinued treatment prior to receiving the second study intervention administration without evidence of inadequate testosterone suppression (testosterone measurement ≥ 50 ng/dL)
The testosterone values of these participants will not be considered for the main analysis (principal stratum strategy).

(d) ICE 4 - Subjects received a prohibited medication during the study
Prohibited medication with impacts on the testosterone value will be identified through blinded data review. Subjects receiving identified prohibited medication (for example, finasteride, dustasteride, or abiraterone) will be included in the primary analysis as non-responder. In contrast, all testosterone measurements from subjects receiving prohibited medications other than identified ones during the study will be included in the primary analysis (composite strategy).

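### Does the FAS rule that keeps observed failures among incomplete men undermine the stated 90% power?

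*SAP*

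**What the plan says.** SAP 2.3 and Protocol 9.2 share one sample-size text. The planning sentence reads: "Considering an observed castration maintenance in 97% of participants, 130 eligible participants are required to demonstrate the efficacy", with about 90% power, one-sided alpha 0.025 and an exact binomial test. Success means a lower 95% limit above 90%. The allowance for loss follows: "Considering a drop-out rate of 10%, 145 participants will be included in the study". Protocol 9.4.2 names Clopper-Pearson for the interval.

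The primary analysis uses the FAS (SAP 5.7.2.2). SAP section 4 and Protocol 9.3 define the FAS as consenting men who "received two administrations of study intervention and completed all visits for testosterone measurement", listing the seven endpoint days, and then add the Note: "a participant will be included in the FAS if his testosterone measurement is ≥ 50 ng/dl". The intercurrent-event rules in SAP 5.7.2.1 have the same asymmetry. ICE 2, for example, removes "Subjects with at least one planned testosterone measurement missing on or prior to Day 337 without evidence of inadequate testosterone suppression", so a man with a high value is not removed.

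The estimand population is worded differently in the two documents. Protocol section 3 restricts it to men "that have received two scheduled treatment intervention doses (i.e. Day 1 and Day 169) and have completed all visits for measurement of testosterone"; SAP 5.7.2.1 refers only to the eligibility criteria. The SAP 2.1 hypothesis concerns the "percentage of participants castrated (serum level of testosterone <1.735 nmol/L) from date of first dose to Day 337".

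**The concern.** Dividing 130 by 0.9 assumes that loss thins successes and failures alike. Under the FAS rule it does not: a castrate man who leaves disappears, while a man who fails and then leaves stays. The FAS rate is then below the rate in all treated men. With 130 analysed the trial can afford only six failures, so small shifts in who is counted move the power.

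Three gaps in the text add to the doubt:

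- The 97% is tied to eligible participants, a term that matches no analysis set.
- The 10% is called drop-out, yet ICE 2 also removes a castrate man with a single missing endpoint sample.
- The Note names no visits, so a high value on Day 3, 7, 171 or 175 could be read as bringing an incomplete man into the FAS, although the endpoint uses seven other days.

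If all this mattered, the trial would be less likely to succeed than its readers were told.

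**Working it through.** **Inputs from the documents.** Null rate 0.90, assumed rate 0.97, 130 analysed, 145 included, 10% loss, Clopper-Pearson lower limit above 0.90.

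**Assumptions not in the documents.** All 145 men are treated. Loss is unrelated to outcome unless stated otherwise. A share *s* of the failures among lost men is seen before they leave; it can lie anywhere from 0 to 1. If the first failing visit and the first missed visit are independent and uniform over the seven visits, *s* = 21/49 = 3/7.

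**Step 1: the plan's own figure.** At n = 130, six failures give a lower limit of 90.2% and seven give 89.2%, so at most six are allowed.

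- Power: P(Bin(130, 0.03) ≤ 6) = 0.903.
- Type I error: P(Bin(130, 0.10) ≤ 6) = 0.021.
- Inclusion: 130/0.9 = 144.4, rounded up to 145.

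The stated 130, 145 and approximately 90% are correct on their own terms.

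**Step 2: the FAS rule.** With rate *p* in all treated men and loss *d*, a man enters the FAS as

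- an observed failure, with probability pf = (1 − p)(1 − d + d·s);
- a complete success, with probability ps = p(1 − d).

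The FAS size is n ~ Bin(145, pf + ps), and failures given n are Bin(n, pf/(pf + ps)). Success requires failures ≤ c(n), the exact limit at that n. For p = 0.97, d = 0.10, s = 3/7: pf = 0.03 × 0.94286 = 0.02829 and ps = 0.873. The expected FAS is 145 × 0.90129 = 130.7 and the FAS rate is 0.873/0.90129 = 96.9%.

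| Case (145 men, 10% loss) | Power at 97% | Type I error at 90% |
|---|---|---|
| Fixed n = 130 | 90.3% | 2.1% |
| Random n, no FAS rule (s = 0) | 88.9% | 1.8% |
| FAS rule, 97% in all treated men, s = 3/7 | 86.9% | 1.25% |
| FAS rule, 97% in all treated men, s = 1 | 84.1% | 0.74% |
| FAS rule, 97% is the FAS rate, s = 3/7 to 1 | 88.9% to 89.0% | not applicable |

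In the last row the rate in all treated men is 97.1% to 97.3%.

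**Step 3: splitting the gap.** Random n costs 90.3 − 88.9 = 1.4 points whatever the FAS rule. It arises because exact-test power is a sawtooth in n: 82.1% at 126, 91.1% at 127, 87.1% at 140. The rule itself costs 88.9 − 86.9 = 2.0 points at s = 3/7 and 88.9 − 84.1 = 4.8 at most, and only on the all-treated reading.

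**Step 4: loss related to outcome.** Hold the overall rate and s = 3/7, and let lost men fail more often than completers. The FAS rate equals the overall rate when the failure ratio is about 1.86 at a true 97% and 1.75 at a true 90%. Type I error reaches 2.5% at a ratio of about 2.6.

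**Step 5: more loss than 10%.** On the all-treated reading with s = 3/7, power is 85.1% at 12% loss and 81.7% at 15%. With 97% in the analysed set and no effect of the rule, 15% loss gives 85.3%. Most of that fall is the ordinary result of losing more men than planned.

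**Step 6: narrowing the Note to the seven endpoint visits.** SAP 6.1 assigns every value from D2+5 to D2+45 to Day 175, which is not an endpoint visit. Protocol 7.2 withdraws a man on two consecutive high values at least two weeks apart, at scheduled or unscheduled visits. A man high at D2+6 and again at D2+21 would be withdrawn with both values in that window. The Note as written keeps him. Lacking his later endpoint visits, he cannot be castrate at all seven, so he counts as a failure. A narrowed Note would remove him and raise the observed rate.

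**The case for a change.** The strongest case for a change is that the documents do not settle whose rate the 97% is. Protocol section 3 describes completers, and if loss is unrelated to outcome the completer rate equals the all-treated rate, so that reading also leads to 87%. The two documents word the estimand population differently, and the sample-size text never mentions the FAS rule. Putting this right would take a few words and no extra men.

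Most of that is true as description, and a sentence naming the set for the 97%, and saying whether the 10% covers missing samples, would do no harm. But the text attaches the 97% to the 130 men left after drop-out, who are the men analysed, and on that reading nothing material is missing. A replacement such as about 87%, range 84% to 89%, would write an undocumented timing assumption into the plan. The only timing evidence in the documents is not uniform: Protocol 4.2 reports that in the earlier subcutaneous study, in men not castrated at entry, failures followed the first injection. The range also holds total loss at 10%, although ICE 2 is part of the complaint.

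Two related suggestions do not change this. Principal stratum is a loose label for complete cases plus observed failures, but the rule beneath it is explicit and renaming it alters no result. Primary-S3 states no interval method, which analysts can supply without touching the primary result; all three sensitivity analyses already use the ITT set.

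**Conclusion.** No change is needed. The plan's 130, 145 and approximately 90% reproduce. With 97% as the rate in the analysed set, power is 88.9% to 90.3%. A fall to about 87% (84% to 89%) requires both that the 97% describes all treated men and an assumption about failure timing that the documents do not make; it also holds total loss at 10%. Even then the difference from the fixed-n figure is 90.3 − 86.9 = 3.4 points, of which 1.4 have nothing to do with the FAS rule.

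The rule is a fair trade-off. It keeps men withdrawn for failure under Protocol 7.2 in the primary analysis, and when loss is unrelated to outcome it makes a false success less likely (1.25% or less under the timings with s of 3/7 or more, against 1.8% without it). That protection weakens if lost men fail much more often than completers; under the s = 3/7 model, type I error passes 2.5% only above about 2.6 times. The unnamed visits in the Note are best left broad, since narrowing them to the seven endpoint days could remove confirmed failures. What remains is a gap in labelling the planning assumptions, which affects no analysis or decision.

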5 STATISTICAL METHODS/ANALYSES

The statistical analyses will be performed in accordance with ICH E9 guideline and guidelines presented in section 9.

5.1 General Considerations

All tables, listings and figures will be produced, and statistical analysis performed using the Statistical Analysis System® software version 9.4 or a later version.

5.1.1 Outputs Presentation

5.1.1.1 Presentation of Visits / Timepoints

For by-visit summaries, the nominal visit as collected in the Electronic Case Report Form (eCRF) will be used in general for analysis purpose unless stated otherwise. Analysis visit window described in Section 6.1 will be used for slotting actual testosterone and prostate-specific antigen (PSA) assessment dates into planned schedule. Unscheduled visits will not be displayed in summaries but will be listed.

Visits in the TFLs will be presented as follows and in the following order:

Period	Long Visit Name	Short Name	Protocol Time Interval
Screening	Day -28 to Day – 1 (Screening)	Scr	
Intervention Period	Day 1 (Baseline)	Bsl	
	Week 1 – Day 3	D3	Day 3 after first injection
	Week 1 – Day 7	D7	Day 7 after first injection
	Week 4 – Day 29	D29	±3 day
	Week 12 – Day 85	D85	±3 day
	Week 20 – Day 141	D141	±3 day
	Week 24 – Day 169	D169	±3 day
	Week 25 – Day 171	D171	Day 3 after last injection
	Week 25 – Day 175	D175	Day 7 after last injection
	Week 36 – Day 253	D253	±3 day
EoS/ED	Week 44 – Day 309	D309	±3 day
	Week 48 – Day 337	D337	±3 day

5.1.2 Descriptive Statistics

Due to the single-arm nature of the study, all statistical analyses will be descriptive. All raw and derived variables will be listed and described using summary statistics. For categorical variables, summary statistics will be displayed using descriptive statistics by frequency count and percentages by category. The missing category will be presented if applicable. Unless otherwise specified, participants with missing data will be included in the calculation of percentages. For quantitative variables, summary statistics will be displayed using descriptive statistics by number of observations, mean, standard deviation (SD), first quartile, median, third quartile, minimum and maximum. Frequency and proportion of missing data will be displayed.

Associated Procedure / Instruction Reference	319480-SOP
Form Reference	080091-FOR v7.0

For the efficacy analyses, the descriptive statistics of treatment effects and corresponding 95% CIs for the primary endpoint and secondary endpoints will be presented if applicable.

5.1.3 *Baseline Value*

Unless otherwise specified, baseline is defined as the last non-missing measurement taken prior to first Investigational Medicinal Product (IMP) administration (including unscheduled assessments).

5.1.4 *Reference Start Date and Study Day*

Reference start date is defined as the day of the first IMP administration.

The day of the first IMP administration will be Day 1. Study day will be calculated as:

- The difference between the event date and the reference date plus one day, if the event is on or after the reference date.
- The difference between the event date and the reference date, if the date of event is prior to the reference date.

Study day will appear in any listings where an assessment date or event date appears.

In case of partial or missing event date, study day will appear missing while any associated durations will be presented based on the imputations described in [Appendix 2](#).

5.2 **Enrolment, Disposition and Analysis Sets**

A Listing presenting study treatment dispensation details will be provided (Listing 16.1.7).

Following disposition summaries will be provided:

- Summary table with the number and percentage of participants screened, screen failed, reason for screen failures, enrolled, treated, having completed the study, withdrawn and reason for withdrawal,
- Summary table with the number and percentage of participants enrolled per visit,
- Summary table with the number and percentages of participants screened and enrolled per country and site,
- Summary table on duration of subject participation in the study,
- Summary of the number and percentage of participants in each analysis set based on all screened participants with reasons for exclusion from each analysis set (see section [5.3](#) about the Protocol deviations leading to the subject exclusion from the PP set).

Following listings will be provided:

- Listing of participant disposition including screen failure participants, and withdrawal participants,
- Listing of dates of visit including duration of subject participation for the enrolled participants,
- Listing including flag for each analysis set and reason for exclusion from each set.

5.3 **Protocol Deviations**

An exhaustive list of major protocol deviations that may occur during the course of the study and any action to be taken regarding exclusion of participants from the PP set is defined in

Associated Procedure / Instruction Reference	319480-SOP
Form Reference	080091-FOR v7.0

IPSEN GROUP

CONFIDENTIAL

D-FR-52014-245

SAP Final: Version 1.0: 30 January 2023

PAGE 15/43

Protocol Deviation Specifications. The protocol deviations related to Coronavirus Disease 2019 (COVID-19) will also be considered. The list of protocol deviations impacting the PP set will be reviewed prior to database lock. The list may be updated, up to the point of database lock, to include any additional major protocol deviations impacting inclusion in the PP set.

Following protocol deviation summary and listing will be provided on the enrolled set:

- Number and percentage of participants with major protocol deviations by deviation category (see DV section of Standard Study Data Tabulation Model (SDTM) user guide).
- A listing of all major protocol deviations.

